Sixteen to twenty-four high schools and surrounding towns within the 14-county Cherokee Nation reservation in northeast Oklahoma will be purposively selected based on school and community characteristics (e.g., size of high school, distance between towns, existing prevention program), stratified by risk profile, and randomly assigned to study condition: (1) preventive intervention or (2) delay-program control. In-person meetings will be conducted with project leadership and school leadership (school district superintendents and high school principals). PIs will present study details and invite the school leadership to participate in the study and to sign a cooperative agreement form. If the high school within a selected town refuses to participate, a replacement town will be selected from within risk strata. Given our recruitment history, we anticipate a very high participation rate—our recent prevention research project with the Cherokee Nation resulted in a 100% school participation rate.

Prevention Program Overview

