School district superintendents and high school principals will be asked to sign cooperative agreement forms to participate in the study. As with our previous school-based projects, school-based screening, brief intervention and referral (CONNECT program), conducted by Cherokee Nation Behavioral Health counselors, will be treated as part of the participating schools' prevention programs. According to Oklahoma State statute (Stat. tit. 63 § 2602. Right of self-consent) a minor may consent to services for the prevention, diagnosis and treatment of drug and substance or alcohol abuse treatment. In addition, the Oklahoma Department of Public Health trains school nurses to provide health education and counseling to help prevent tobacco use, alcohol use, substance abuse, and other health related issues. The CONNECT school-based prevention program is consistent with the laws and standards of practice in Oklahoma. Cherokee Nation Behavioral Health (CNBH) youth services provides a central hub connecting youth and their families to programs, resources and services. The CNBH CONNECT coaches will introduce and support the CONNECT program. Each semester, a computer-based CONNECT screening and brief intervention will be implemented universally, to reduce potential stigma and to reinforce drug-free norms among all students. Universal screening avoids contributing to harmful, negative stereotypes likely to result from singling out students. The computer-based universal screening and brief intervention will be supported by either one or two Connect Coaches. As originally planned, follow-up of moderate to high-risk youth will be conducted by a Connect Coach through Zoom, other electronic communication, or in-person visits, with referral to Cherokee Nation or community services if deemed necessary.

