The evaluation of the prevention programs will be accomplished through self-report surveys of a cohort of high school students followed over three years, from grade 10 (ages 15-17) to the year following high school graduation (ages 18-20). A pilot survey will be administered in the study schools using all approved protocols in grade 9. The main outcome analysis will include baseline (fall of 10th grade) through spring of 12th grade surveys. A secondary outcome analysis will include the six-month follow-up survey conducted six months post on-time high school graduation.

Recruitment Procedures

All 10th grade students enrolled in the participating study high schools will be eligible to participate in the study. As a universal preventive intervention, and given the need for a community-wide representative sample, there are no exclusionary criteria. Beginning in 10th grade, a cohort of high school students will be asked to participate in a brief, 20-30-minute, web-based survey on health behaviors two times per year. The survey will be administered using REDCap or Qualtrics on cellular-connected project tablets and implemented during homeroom, a class period, lunch period, or at

another time convenient to each school and participant. All data will be encrypted as soon as it is entered and transmitted to a central server at Emory University. No school personnel will be involved in any survey administration tasks, avoiding any potential risks and biases that could accrue from the involvement of school personnel in survey administration.

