Our recruitment and retention protocol requires careful planning and treating school leadership, parents and study participants with respect and courtesy. Our previous trials demonstrate this has worked well—we have consistently been able to recruit a substantial percentage of the sample and have experienced few refusals. As with all field studies, recruiting students and parents/guardians in this fashion necessarily introduces potential selection bias because those who participate may be systematically different from those who decline. However, maintaining a respectable baseline participation rate, conducting descriptive analyses to determine whether the final sample is representative of the school demographically and to ensure comparability on relevant characteristics between communities, and weighting to adjust for nonresponse helps offset the effects of selection bias. Also, bias will be somewhat further reduced by providing financial incentives and maintaining direct contact with schools, parents and students.

Measures

The Youth Experiences Survey is attached. It will be used to collect data from youth participants to assess substance use and related risks/harms, perceived availability of opioids and other drugs, knowledge and perceptions of consequences, values and beliefs about substance use, social normative beliefs around substance use, social skills and social support.

Each participant will be asked to complete a Contact Information Form during the final school-based survey in Spring 2024. The contact form will be a scannable paper form, separate from the tablet-based student survey, and students will be provided \$5. The form asks about contact information to help us

maintain contact and reach participants for the follow-up survey. We will ask youth to provide phone numbers, email address, and home address. The Contact Information Form is attached. Mid-summer we will contact participants via text, call, or email to ask for confirmation of contact information. A \$10 electronic Visa or gift card will be provided for confirming contact information.

III. Risk/Benefits

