The data-gathering requirements and intervention activities of the proposed research pose no more than minimal risk to participants. The surveys will be designed to be of limited distress, although a student may be uncomfortable answering certain questions. The surveys are short—average completion time is expected to be 20-30 minutes. Participants will be reminded at the beginning of the survey that they are free to skip any questions or to stop the survey at any time. Our confidence in terms of the measures to be used is based on many years of experience in using these surveys. Moreover, students have reported a high level of comfort with the surveys and assessments in the past. Although rare, there is a possibility for the surveys to produce some stress or frustration, which will be carefully monitored. Thus, at most, participants may find these assessments boring, annoying, or frustrating.

There is potential for significant direct benefits of this project to participating adolescents and young adults; the evidence-based interventions are expected to improve several outcomes under study, such as preventing the onset and escalation of drug use and related risks/harms. The control sites will be offered the intervention materials at the end of the study, as well as the opportunity for teacher and staff trainings provided Cherokee Nation Behavioral Health during the active study phased (e.g., bullying prevention training).

The minimal risk of a breach of confidentiality, plus possible discomfort that may accompany some behavioral change efforts, is easily outweighed by the likely benefits.

IV. Data Security/Monitoring

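### Could a school refuse, or a replacement town enter the trial, after the arm is known?

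*Combined protocol and SAP*

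**What the plan says.** The Sample paragraph of section II opens with the selection of sites: "Sixteen to twenty-four high schools and surrounding towns within the 14-county Cherokee Nation reservation in northeast Oklahoma will be purposively selected". The same sentence goes on to say that the towns are "stratified by risk profile, and randomly assigned to study condition: (1) preventive intervention or (2) delay-program control". The next sentences describe in-person meetings with superintendents and principals, at which the investigators "invite the school leadership to participate in the study and to sign a cooperative agreement form". The refusal rule comes next: "If the high school within a selected town refuses to participate, a replacement town will be selected from within risk strata". The paragraph closes by expecting very high participation, because every school took part in the team's recent project with the Cherokee Nation.

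The agreement is mentioned again at the start of Prevention Program Overview: "School district superintendents and high school principals will be asked to sign cooperative agreement forms to participate in the study". That sentence does not date the signature relative to assignment either.

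Three other statements bear on the point. On the analysis: "The main outcome analysis will include baseline (fall of 10th grade) through spring of 12th grade surveys". On timing, under Measures: "Each participant will be asked to complete a Contact Information Form during the final school-based survey in Spring 2024". On what control schools receive, under III. Risk/Benefits: "The control sites will be offered the intervention materials at the end of the study". That last sentence also offers control sites staff training while the study is running.

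**The concern.** In the order of the sentences, towns are selected, stratified and randomised; then leaders are invited; then refusers are replaced. If the trial ran in that order with the arm disclosed, two things could go wrong. A school might decline because of the arm it drew. Its substitute might then take over that arm without having been randomised.

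The arms do differ for a school. Intervention schools host screening every semester, while control schools are offered the intervention materials when the study ends. Initial selection is purposive, and no random draw is specified for replacements within a stratum, so discretion is not ruled out.

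With so few clusters, school-level randomisation is the main protection for the comparison. The mixed model and multiple imputation in V. Data Analysis deal with clustering and missing surveys; they do not undo selection of schools after assignment. To the extent the model uses the fall 10th-grade baseline, a stable difference in level between refuser and replacement would be partly absorbed. A difference in trend would not.

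**Working it through.** The plan states no figure on this point, so there is nothing to reproduce. The check has two parts: what the wording supports, and how large the effect could be.

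**Wording, set side by side**

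- The assignment sentence is a one-line summary of the design. The sentences after it explain how sites are recruited. No word such as *then*, *after* or *once assigned* links them.
- The refusal rule speaks of a town that was selected, not one that was assigned. The substitute is also selected, which is the verb of the first step.
- The substitute comes from within risk strata. No arm is mentioned.
- The number of schools is still a range, which suits a list that is not yet closed.
- Prevention Program Overview repeats the request to sign and adds no timing.

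The text is therefore compatible with selecting, signing, replacing and then randomising. It does not prove that order. How a replacement is chosen is partly given (same risk stratum); what is unstated is its arm and the draw within the stratum.

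**Size, if the unfavourable order had been used**

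Inputs from the protocol: n = 16 to 24 schools; 100% school participation in the earlier project. Assumptions: equal arms of 8 or 12; independent refusal at rate q per school; a replacement's change from baseline differs from the refuser's by d = 2 to 5 percentage points.

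1. Weight of one school in its arm: 1/12 = 8.3% to 1/8 = 12.5%.
2. Shift in the arm difference per replacement: d × weight, from 2/12 = 0.17 to 5/8 = 0.63 points.
3. Chance of at least one refusal, 1 − (1 − q)^n, and expected number of replacements, nq:

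| q (assumed) | P(at least one), n = 16 | P(at least one), n = 24 | nq, n = 16 | nq, n = 24 |
|---|---|---|---|---|
| 0% | 0% | 0% | 0 | 0 |
| 1% | 14.9% | 21.4% | 0.16 | 0.24 |
| 2% | 27.6% | 38.4% | 0.32 | 0.48 |
| 5% | 56.0% | 70.8% | 0.8 | 1.2 |
| 10% | 81.5% | 92.0% | 1.6 | 2.4 |

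4. Upper bound on the expected shift, if every replacement moves the result the same way: nq × d/(n/2) = 2qd, so n cancels. With d = 5, this is 2 × 0.02 × 5 = 0.2 points at q = 2%, 0.5 at 5% and 1.0 at 10%. With d = 2, it is 0.08, 0.2 and 0.4 points. At q = 0 it is zero. If refusal and replacement work alike in both arms, the shifts cancel on average.

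**Timing**

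The last in-school survey, in spring of grade 12, is dated Spring 2024. Grade 12 is then 2023–24 and grade 10 is 2021–22, so baseline falls in about fall 2021. Re-sequencing recruitment is probably no longer possible.

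**Cost of a sensitivity analysis without replacements**

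If between-school variance dominates, dropping one school multiplies the standard error by √[(1/7 + 1/8)/(2/8)] = 1.035 with 8 per arm, or √[(1/11 + 1/12)/(2/12)] = 1.022 with 12 per arm. With no replacements, the analysis is empty.

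**The case for a change.** The best case for a change is that the plan does write a replacement rule, and a rule that can decide which clusters enter which arm ought to be complete. Past participation of 100% is an expectation, not a guarantee: at an assumed 5% refusal rate, at least one replacement is more likely than not. Setting out the order would take a sentence or two, and the potential harm touches the randomisation itself.

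Part of this stands. The documents do not say whether leaders knew their arm when they were asked to sign, or how a substitute received its arm. If refusals did follow a known assignment, later modelling would not repair it.

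The rest is weaker. A refusal alone does no harm; it must come after a disclosed assignment and lead to replacement that differs by arm. Nothing in the documents points that way, and the training offered to control sites during the study reduces the incentive to decline that arm. The figure just above the Sample heading is missing from the text available here and may show the sequence. The suggested analysis would have nothing to exclude if no school refused; if some did, dropping their replacements would not recover the refusing schools.

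**Conclusion.** This is a gap in description that analysts fill sensibly, not a flaw in the design. The Sample paragraph can be read as agreement and replacement within risk strata followed by randomisation, and on that reading the concern disappears.

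On the other reading, the expected effect is zero at the participation the team has already achieved. Under the assumptions above it is at most 0.2 points at 2% refusal and 1.0 point at 10%, the latter far from the very high participation expected. These figures rest on equal arms, an assumed 5-point difference in trend, and every replacement pulling the same way. The documents support none of those values directly, so the figures show scale only.

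The recruitment dates make a new sequence largely moot. The order of agreement and assignment, and the handling of any replaced school, belong in the account of school flow in the outcome paper. The planned analysis does not depend on amending the protocol first.

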All 10th grade students in all participating high schools will be recruited. Participating schools will provide the researchers with a list of the most current home addresses and telephone numbers for all students in the participating high schools. Parent consent letters will be sent home by Emory University and the Cherokee Nation, describing the study and its importance and providing a toll-free and local telephone number that parents/guardians can call with questions or concerns. In-person visits will be made when requested or if the parent is unavailable via phone. Parents will be asked to respond by returning an addressed postage-paid postcard or calling Cherokee Nation Behavioral Health using toll-free telephone numbers, if they refuse permission for their son or daughter to participate. Also, each adolescent/young adult participant will be given the opportunity to decide not to participate, and may withdraw their participation at any time. Students will be provided \$5 for each biannual survey implemented within schools. For the six-month follow-up survey, planned for Fall 2024, administered outside of school, a \$50 electronic Visa or gift card will be provided. A number of steps will be taken to maximize participation and retention rates. The fact that the intervention and assessments proposed in this application will be endorsed by the Cherokee Nation and school leadership at the participating high schools will help maximize participation rates. Youth will receive reminders and compensation for their time. For youth who are missing from school during survey administrations, tactics to reach them for follow-up surveys may include emailing and texting to ask how they are, update social media, email, phone and other contact information, and reminding them about an upcoming survey. We will use procedures for tracking and follow-up surveys as we implemented in a long-term follow-up of a cohort of youth in Chicago, including secure internet and in-person survey administration options. Although some attrition is anticipated, a substantial proportion of the students recruited at baseline are expected to be retained in the study. In our previous prevention trial in the Cherokee Nation, we maintained over 80% participation across the three-year study.

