Data collectors will be professional staff with training in Human Subjects Research. They will be thoroughly trained in the principles of the study and use of the survey methods. They will also be qualified to interact with adolescents, parents, and school administrators. Drs. [name] and [name] will coordinate and train on collection of survey data. An Evaluation Field Supervisor will oversee all field activities, including administration of assent forms, coordination with schools and teachers, and administration of assessments. The tracking and assessment databases will be linked by arbitrarily-assigned study numbers (not school ID or other such numbers) to ensure identifying information is not contained in the assessment databases. Data collected for the study will be transmitted immediately via cellular-connected tablets using REDCap or Qualtrics to the Emory University server where checks will be run for data consistency and quality. It is important to note that the schools will not obtain or maintain any individual-level survey results and research staff will not retain any identifying information; thus there will be no way to link names with survey results. Processes are in place to generate de-identified databases and statistical programs for analyses.

Prior to any member of the research staff initiating contact with research participants, they will be trained in the following areas: 1) Protecting human study volunteers in research in accordance with Emory and Cherokee Nation IRB requirements; 2) Understanding the project grant (background, application, and aims); 3) Demonstrated understanding of data collection forms; 4) Understanding how all forms are filed, both electronic and material (i.e. exact location, computer drive, folders, and which

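### Does collecting contact details on one paper form, at the last in-school survey, leave absentees and early leavers out of the six-month follow-up?

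*Combined protocol and SAP*

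**What the plan says.** Measures (combined protocol and SAP, section II) sets the timing: "Each participant will be asked to complete a Contact Information Form during the final school-based survey in Spring 2024". It also sets the mode: "The contact form will be a scannable paper form, separate from the tablet-based student survey". The form asks for telephone numbers, an email address and a home address, and its purpose is to help staff reach participants for the Fall 2024 survey. A second step follows: "Mid-summer we will contact participants via text, call, or email to ask for confirmation of contact information".

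Recruitment Procedures describes other routes to the same information:

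- "Participating schools will provide the researchers with a list of the most current home addresses and telephone numbers for all students".
- For youth missing from school at a survey, tactics "may include emailing and texting to ask how they are, update social media, email, phone and other contact information".
- Tracking and follow-up will use the procedures of an earlier long-term cohort, "including secure internet and in-person survey administration options".
- On past performance in the previous Cherokee Nation trial: "we maintained over 80% participation across the three-year study".

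IV. Data Security/Monitoring shows that a tracking database exists: "The tracking and assessment databases will be linked by arbitrarily-assigned study numbers". V. Data Analysis commits the study to extensive tracking into the year after expected graduation, and to multiple imputation from all available outcome data. The evaluation paragraph under Prevention Program Overview places the six-month survey in a secondary outcome analysis only.

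**The concern.** A form meant to keep the study in touch with people who leave school is offered at the one wave that early leavers cannot attend and absentees miss. It is also on paper, although surveys may be taken by electronic link when school administration is not feasible. No make-up, mailed or electronic version is described.

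The six-month survey is the only wave after high school, and the introduction presents that transition as an advance on the previous trial, which ended at age 18. If students without a form are reached less often and use drugs more, loss at that wave is selective and observed prevalence is too low. If the pattern also differed between arms, the secondary comparison would be biased.

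**Working it through.** **Wave count.** Fall of 10th grade to spring of 12th grade is 3 school years with 2 surveys each: 3 × 2 = 6 in school. Adding the six-month follow-up gives 7, which agrees with the plan's figure of about seven data points per student. The form is therefore offered at 1 of 6 in-school waves, the last. The grade 9 pilot is not counted.

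**What a student without a form lacks.**

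| Item on the form | Other described source |
|---|---|
| Home address | School list (all students) |
| Telephone numbers | School list; updating for youth missing from school |
| Email address | Updating for youth missing from school; no first source named |

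Two of the three items come from the schools. The third can be asked for by telephone, by text or in person. Nothing limits the mid-summer contact to students who completed the form.

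**How many students.** The documents give no figure. If the previous trial's participation applied to Spring 2024 (an assumption), the share without a form would be under 100% − 80% = 20%. This counts students without a form. It does not count students who cannot be found, and it may include refusals, which no form would recover.

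**Possible size at the follow-up, before imputation.** Let *m* be the share without a form, *k* their chance of being reached relative to others, and *d* their excess drug use in percentage points. Their share among respondents is

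*s* = *mk* / ((1 − *m*) + *mk*),

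and observed prevalence is too low by (*m* − *s*) × *d*. The values of *k* and *d* are assumed, and so are the smaller values of *m*.

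- *m* = 0.20, *k* = 0.5, *d* = 10: *s* = 0.10/0.90 = 0.111, so (0.200 − 0.111) × 10 = 0.89 points.
- *m* = 0.20, *k* = 0.75, *d* = 10: *s* = 0.15/0.95 = 0.158, so 0.42 points.
- *m* = 0.10, *d* = 10: 0.47 points at *k* = 0.5 and 0.23 at *k* = 0.75.
- *k* = 1 or *d* = 0: 0 points.

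The arm contrast shifts by the difference between the two arms' understatements. With equal *m*, *k* and *d* this is 0. On this grid the extreme is one arm at *k* = 0.5 and the other at *k* = 1, which gives 0.89 − 0 = 0.89 points. The documents describe the same tracking in both arms and give no mechanism for such a split.

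These figures precede the planned multiple imputation. A student who missed Spring 2024 may still have up to 6 − 1 = 5 earlier waves of outcome data to impute from.

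**What an added offering in fall of 12th grade would gain.** With 20% absence per wave and correlation φ between absences, the share missing both is 0.20² + φ × 0.20 × 0.80:

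- φ = 0: 0.04 (4%)
- φ = 0.5: 0.04 + 0.08 = 0.12 (12%)
- φ = 1: 0.04 + 0.16 = 0.20 (20%, no gain)

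Absence is likely to recur in the same students, so the 4% figure is optimistic. Students who left before that term gain nothing.

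**The case for a change.** The best case for a change is that the other routes are weaker than the form. The updating of contact details for absent youth is something the plan says may be done, and it needs a working contact to begin with. The school list appears in the recruitment text with no stated refresh and contains no email addresses. The mid-summer step asks for confirmation, which suits details already held. The extensive tracking is not itemised. The participation figure comes from a trial that ended at 18, so it says little about Fall 2024. The protocol itself argues, about written parental consent, that nonresponse is concentrated in the students most at risk; that is an analogy, but it makes a gap in drug use plausible.

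Much of this stands as description. The plan does not name a first source of email addresses for students without a form, and it does not mention early leavers separately. It does not stand as a reason to alter the schedule:

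- The use of tracking procedures with internet and in-person options is a firm commitment.
- An electronic form can be sent only to someone whose contact details are already known, so it adds little for those hardest to find.
- An added wave does not help students who left before it. It also holds identifiers longer under a waiver of written parental consent and needs IRB review.
- Collection at the last school contact has a merit of its own: the details are the most recent available before the follow-up.

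The statement under IV. Data Security/Monitoring that research staff keep no identifying information sits awkwardly with the contact form and with the list linking study IDs to names. That is a separate point of confidentiality wording. It does not depend on when the form is given and changes no result.

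**Conclusion.** No change to the plan is needed. The observation is correct as far as it goes: one paper administration, at the sixth of six in-school waves, with no stated make-up. It shows a gap in one form. It does not show that contact details are lacking for the students concerned, since the plan describes several other ways to hold or update them, and staff following those procedures would ask absentees and early leavers for the same items.

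The main outcome analysis is unaffected. For the secondary six-month analysis, the illustrated understatement of prevalence is 0 to 0.9 points before imputation, and the arm contrast does not move if the arms are alike. That range rests on a 20% share carried over from another trial and on assumed values for reach and excess drug use. The true effect cannot be derived from the documents and may be zero. The form and the survey are attachments that were not available, so contact details may also be collected earlier than the text shows.
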